PROTOCOL

NANOPULSE SEBORRHEIC KERATOSIS STUDY (NP-SK-002)

**March 17, 2017
Rev. 4/17/17
Rev. 4/28/17
Rev. 7/14/17**

CONFIDENTIAL

BACKGROUND

The Pulse TX is a medical device intended to clear the skin of benign, undesired skin lesions as an alternative to surgery and other more ablative methods for removing benign lesions. The system is designed to deliver a timed series of very low energy, high voltage (less than the voltage of static electricity) pulses of a time length between 100 and 750 nanoseconds (billionths) of a second. The non-thermal effect on tissue takes place in a very shallow depth of skin directly below the sterile treatment tip. The device emits significantly less energy than existing laser, electro-surgery or electro-cautery equipment.

Extensive *in vitro* research demonstrates a stimulation of a programmed cell death called apoptosis in a treated area, which is one of the presumed mechanisms for observations of clinical and histologic changes to cells in multiple studies of *in-vivo* treated tissue. In animal studies with over 1000 rats and mice, nano-pulsed devices have been demonstrated to reduce or eliminate benign tumors with a clinically acceptable margin of safety. A pilot clinical trial was conducted under IRB oversight in 2012 with a similar version of the Pulse TX device, with the findings published in *Experimental Dermatology*. (See Attachment A) A total of ten basal cell carcinomas on the skin of three Subjects were treated with a range of settings. Seven of the ten lesions were free of basal cells at the conclusion of the study, two partially resolved, and one recurred. No scars were visible at the healed sites of any of the successfully treated lesions.

PRIOR CLINICAL INVESTIGATIONS

Study Name:	NanoPulse Human Tissue Study
Study Number:	NP-ABD-001
Device Named:	Pulse TX System
PI Name:	[name]
Co PI:	[name]
Study Dates:	November 2016 to January 2017

A total of seven subjects participated in this prospective, single site, non-randomized study. All of the participants were females representing several Fitzpatrick Skin Tone Classifications, and ranging from the low 40's to middle 60's in age.

The study was comprised of two sequential segments. The first segment called for the serialized use of the test device in specific locations on intact abdominal skin predetermined to be resected during a standard abdominoplasty. The primary endpoint of the first segment of the study was to establish that the trauma to the tested skin would be minimal. The appearance of each intact tested tissue location was comparable to that anticipated following any minor surgical insult.

Lidocaine was injected prior to use of the Pulse TX skin exposure. Subjects reported little or no sensation during the treatment session. Subjects further reported little or no discomfort after the Lidocaine effect had diminished. There were no adverse events, no reports of bleeding, and no scarring noted by the investigator at the end of the 60 day study.

The second segment of the study called for the histological analysis of tissue samples prepared from the abdominal section that were resected at the time of the abdominoplasty. Internal and outside expert histologists were consulted. This second segment did not impact the participating subject. Consequently, Pulse Biosciences, Inc. secured IRB oversight concentrated on the first segment of the study. It should be noted however that the histological analysis to date confirms that the Pulse TX was successful in achieving its intended effect. See Attachment B for a Summary Histological Report.

PROPOSED SEBORRHEIC KERATOSIS STUDY

Study Name: Nanopulse Seborrheic Keratosis Study
Study Number: NP-SK-002
Device Named: Pulse TX System
PI Name: [name]
PI Name: [name]
PI Name: TBD
Study Dates: TBD

PURPOSE AND SCOPE OF THE STUDY

The primary purpose of the study is to evaluate the use of the Pulse TX System when used to remove Seborrheic Keratosis (SK) lesions from the non-facial areas of healthy adult subjects. These benign skin lesions are frequently located on the limbs and/or trunk and not considered to be pre-cancerous. Patients routinely seek their removal for cosmetic/aesthetic reasons. SK lesions are typically treated using cryogen or a scalpel, or dessication with a

heat-based energy technology such as a laser or electrosurgery. SKs do not self-resolve without treatment.

STUDY OBJECTIVES

The specific objectives of the study are as follows:

- Document the non-treated appearance of off-face SK's
- Evaluate the clearance of SK's in off-face locations after removal using the Pulse TX System vs. pretreated appearance of the same lesion
- Evaluate the clearance of the treated SK's at various points in time over several weeks following the initial procedure, compared to the pre-treated SK's

PRIMARY ENDPOINT

- The primary endpoint of the study is the degree of clearing of benign SK lesions as rated by the independent reviewer's assessment of photographs of the lesions at the final study visit.
 - A 4-point scale (0, 1, 2, 3) will be used wherein each lesion will be characterized as "Clear", "Mostly Clear", "Partially Clear", "Not Clear".

Photographic Review of SK Lesions Rating Scale			
Clear	Mostly Clear	Partially Clear	Not Clear
0	1	2	3

○ See Attachment C for a protocol specific to the Independent Review.

SECONDARY ENDPOINTS

- A secondary endpoint of the study is the degree of clearing by the final visit as rated by the treating physician's assessment.
 - The same 4-point scale will be used as that used for the Photographic Review.

Investigator Assessment of SK Lesions Rating Scale			
Clear	Mostly Clear	Partially Clear	Not

			Clear
0	1	2	3

- An additional secondary endpoint of the study is subject satisfaction with the SK's area at the final study visit. A 5-point scale (0, 1, 2, 3 4) will be used wherein the Subject will be asked to rate their level of satisfaction with each SK area as "Satisfied", "Mostly Satisfied", "Partially Satisfied", "Dissatisfied" Highly Dissatisfied".

Patient Satisfaction for each SK area at day 106				
Satisfied	Mostly Satisfied	Partially Satisfied	Dissatisfied	Highly Dissatisfied (worse)
0	1	2	3	4

SUCCESS CRITERIA

- Independent Reviewer Assessment of Photograph: A score of "0" or "1" at the last follow-up will represent a successful outcome for that lesion. The study will be considered a success if 65% of treated lesions are reduced by a score of 2 or more points on the lesion scale
- Physician Assessment: A score of "0" or "1" at the last follow-up will represent a successful outcome for that lesion. Success for this criteria is 65% of lesions rated as a 0 or 1 on the scale.
- Patient Assessment: A score of "0" or "1" at the last follow-up will represent a successful outcome for that lesion. Success for this criteria will be 65% of lesion areas evaluated as "Satisfied" or "Mostly Satisfied".
- The overall study will be considered a success if 2 of the 3 criteria listed above are met.

STUDY DESIGN

A prospective, randomized, open label, multi-site, NSR study design where each subject serves as his or her own control will be employed. A Principle Investigator will be identified at each of up to five participating sites. A total of up to 60 Subjects will be consented and enrolled with anticipated enrollment expected to be uniformly distributed across sites. The PI will consider the study inclusion and exclusion criteria and invite appropriate patients to participate in the study.

No significant risk is posed by either the use of the Pulse TX System or the study process. While safety can never be taken lightly, this study is not meant to measure, monitor or analyze any significant disease or disorder for which medical treatment is mandatory. (See additional information regarding Non-Significant Risk statement in the following pages.)

ANALYTICAL METHODS

Three sets of data will be analyzed:

1. Clinical observational data as derived from the examinations.
2. Data captured during the photograph review process.
3. Patient self-reported symptoms and observational data.

The statistical analysis for this single-arm NSR study will be performed after collection of safety, effectiveness and secondary outcomes during the baseline period and each evaluation interval.

- Analysis of primary endpoints in intent-to-treat population
- Analysis of primary and secondary endpoints in the per protocol population
- The calculation of the change from baseline in the treated lesion size and appearance will be adjusted by the observed effect on the untreated lesion change in size and appearance
- Exploratory Data Analysis to describe distributions and to explore trending
- Repeated measures ANOVA or non-parametric equivalent to compare means
- Likelihood ratio statistics to assess categorical data
- Chi-Square Tests to compare binary proportions
- Exact probabilities will be computed for any inferential analysis performed
- 95% confidence levels will be calculated using exact methods
- Agreement statistics to estimate the inter- and intra-photographic reviewer variability
- All analysis will be adjusted for the correlated nature of the data since more than one lesion is being sampled from the host subject

All tables and listings will be produced and stored in SAS datasets. No data imputations will be performed.

SAMPLE SIZE ESTIMATE

A one group χ^2 test with a 0.050 two-sided significance level will have 91% power to detect the difference between the Null hypothesis proportion π_0 , of 0.510 (51%) and the Alternative proportion, π_A , of 0.650 (65%) when the sample size is 135.

DEVICE DESCRIPTION

[figure not shown]
The **Pulse TX System** consists of an electrical pulse generator (similar to devices used to electro-coagulate tissue) combined with a hand-piece which is held by the clinician during application of pulses to the skin surface. The hand-piece is coupled to a sterile, single patient-use treatment tip. The tip has an array of pins no greater than 1.27 mm in diameter (18 gauge) which penetrate the skin between 1 and 3 mm. Power settings within a minimum and maximum range are available for selection by the physician, and are software limited to defined setting for each treatment tip by the sponsor. Once the electrical pulse generator is turned on and a power setting is selected, a foot switch triggers a sequence of pre-programmed electrical pulses to an area of skin directly beneath the treatment tip.

A common commercially available sterile coupling gel is applied to the skin or treatment tip surface to ensure good electrical coupling to the tissue.

The three system components are as follows:

1. **Pulse Generator** including a built-in touch screen for setting selection, a power cord, and a mandatory foot pedal for activation of a pulsing sequence
2. **Hand-piece** (re-usable)
3. Single patient-use **Tip** (five different versions available, described below)

Pulse TX Graphic

Footswitch connector
Locking brakes

Figure 1. Pulse generator

[figure not shown]
Electrode Handpiece

A reusable handpiece allows the operator to connect the single-use patient treatment tip to the generator. One end of the handpiece connects to the generator; the other end connects to the treatment tip. The handpiece can be cleaned and after each use.

Single-use Treatment Tip

A sterile single-use patient Treatment Tip attaches to the hand-piece. The tip delivers the nano pulses to the area to be treated through an array of micro-needles. Five tip sizes are available:

- 2.5 mm x 2.5 mm Treatment tip
- 5 mm x 5 mm Treatment Tip
- 7.5 x 7.5 mm Treatment Tip
- 10 mm x 10 mm Treatment Tip

SITE/INVESTIGATOR SELECTION

Up to 5 study sites will be selected to participate in the study. Two of the five sites have been identified. The additional sites have not yet been determined. The table below provides additional information

NAME OF STUDY SITE	ADDRESS OF STUDY SITE
Site 1: Aesthetic Artistry Surgical and Medical Center or AASMC	[name] T [contact]
[name] [name]	[name] T [contact]
Site 2: Aesthetic Center [name] [name]	[name] T [name]
Same Investigators at alternate location	[name] [contact] T [name]
TBD	
NAME OF STUDY MONITOR	
[name], MSN Consultant, Pulse Biosciences	[name] T [name] F [name] [contact]

Site #1 above will be the first to initiate the study. This site and the Investigators have been approved by BioMed for a study that is currently open but not active. The required forms and information about subsequent sites and Investigators will be provided to BioMed prior to any study related activities at the site in question. Prior to enrolling a Subject at any particular site the investigator and appropriate members of the study team at that site will participate in a comprehensive training program designed by Pulse.

SUBJECT RECRUITMENT AND SELECTION

Convenience sampling will be used to enroll subjects exclusively from the patient population at each of the sites. The planned enrollment is set at up to 15 subjects at each site for a total of 60. Recruitment will be conducted via direct communication between potential Subjects with each PI and/or the designated staff.

The invitation to participate will be extended to those patients who are known or present with SK lesions that they individually choose to have removed. The Informed Consent discussion and signature process will be conducted by the PI and/or the designated staff. Once consented, each Subject will be assigned a unique Study Identification Number. See Attachment D for statistical discussion and analysis of proposed Subject population.

Recruitment Statement

If recruitment is not adequate to meet the study requirements, a counter card or other media format may be used. See Attachment D for a proposed recruitment statement. The study **Inclusion** and **Exclusion** criteria are noted below.

Inclusion Criteria:

- Willing to sign the informed consent
- Males or females
- At least 18 years of age but less than 65 years of age
- Has a clinical diagnosis of stable, clinically typical seborrheic keratosis
- Medically determined candidate for at least 4 off-face SK lesions
- Must have at least four treatable SK's and be willing to have Pulse TX treatments on any three of the four treatable SK's. Treatable SK's must:
 - be at least 1 mm in height, and no greater than 3 mm in height.
 - not have a dimension perpendicular to the longest dimension of greater than 7.5mm or longer in any dimension than 20mm..
- Willing to have three of the designated SK's treated in a single treatment session
- Willing to return to the PI's office for five additional study visits at specified intervals over 106 days
- Agrees to high resolution photos of both the treated SK lesions and the untreated SK lesion
- No subject identity will be possible via the "lesion-only" photograph
- Has no evidence of active infection in the designated tissue prior to treatment

- Is not allergic to Lidocaine or Lidocaine-like products
- Not pregnant or lactating
- In the investigators' opinion, be in good general health and unlikely subject to risks from treatment

Exclusion Criteria:

- Implantable electronic devices. e.g., automatic defibrillator
- Active infection or history of infection within 90 previous days in designated test area
- Not willing or able to sign the Informed Consent
- Non English speaking or reading
- Is known to be immune-compromised
- Known to be keloid producer
- On blood thinning medications
- Diseases, conditions, or situations wherein PI judges that the patient is not appropriate for participation in the study

NON SIGNIFICANT RISK STATEMENT

The proposed study fits the criteria for a non-significant designation for the following reasons:

- Subjects will be recruited for the study strictly on a voluntary basis
- Participation in the study takes approximately 1 hour for the first treatment visit and 30 minutes for each of the five post treatment evaluation visits, which includes photographs of both treated and control lesion(s)
- Localized anesthesia will be used to control discomfort at the time of the test device application.
- After the test device is deployed and the anesthesia is dissipated, there may be mild, localized discomfort at the site of the treatment. A small scab or crust may develop. This occurrence is transient and should resolve without intervention.
- Transient and minor discomfort at the treated site and appearance of a small scab typically occurs when other standard treatments are used, i.e., cryogen to remove SK's. Use of the Pulse TX does not raise any additional concerns compared to current methods of lesion removal
- There is no loss of privacy as no study records will be viewed or retrieved by anyone other than the study team members.

- Protected information will not be captured
- Subjects are protected by a coding system to de-identify them

STUDY PROCEDURE

The following is an example of the Subject related activities to be completed for each Subject in the study. The exact order may differ depending on Subject/PI schedules and preferences.

Activities prior to or on same day as study enrollment and occur on same day as treatment visit:

- evaluation for Inclusion/Exclusion criteria
- sign the consent form prior to any study activities
- receive a copy of the signed consent form

Activities on 1st Study Visit Day

- Four SK's are selected that meet the study criteria for treatable SK's. If more than four lesions are present, the patient can state a preference for which 4 lesions are included in the study
- Photographs of each of the four selected SK's will be taken prior to anesthesia or treatment
- Local anesthesia will be applied to the four selected SK's.
- Using a randomization method, exactly three of the selected SK's will be designated to be treated and one will be designated as an untreated control
- The test device will be deployed to the selected SK's according to the randomized order
- a light bandage will be applied
- Subject will be discharged

Activities on 2nd, 3rd, 4th, 5th and 6th Study Visit Days

- Photographs of each of the 3 treated lesions and one non-treated lesion will be taken
- Each lesion will be clinically assessed and the appearance will be rated according to specified criteria.
- Any adverse events will be identified and documented.

RANGE OF DAYS FOR STUDY VISIT INTERVALS		
STUDY VISITS	TARGET VISIT DATES	VISIT DATE RANGES
1	Treatment Day	NA
2	1 week post TX	7 to 9 days post TX
3	1 month post TX	28 to 35 days post TX
4	60 days post TX	50 to 60 days post TX
5	90 post TX	80 to 90 days post TX
6	106 days post	100 to 111 days post

SUBJECT COMPENSATION

Each subject will be compensated for any inconvenience that study participation may represent. Specifically, each patient will make 6 total visits to the surgeon's office (approximately 4 hrs. total time). In return for this time commitment, the patient will receive \$200 for the treatment visit, \$100 for each of the 5 follow up visits and \$400 bonus for completing all of the scheduled visits. The total amount of compensation will be \$1,100.

STUDY BENEFITS

A volunteer for the proposed study is someone who has elected removal of benign lesion(s). Such lesions are typically removed via cryogen or a scalpel. Participation in the study offers another technique to accomplish the same thing as the typical tools. Experience with the Pulse TX to date offers some confidence that the lesions will be successfully removed although no assurances will be offered. The information learned may contribute to the ultimate use of a more safe and effective device available to ablate tissue in future patients.

STUDY/DEVICE RISKS

The Investigators for the study are experienced physicians. Use of the Pulse TX System poses very minimal risk, including scabbing, minor skin pigment changes or scarring and minor discomfort which can be further minimized by covering the spot with a small bandage. Typical wound complications such as infection, bleeding and discomfort which requires prescription medication for relief are not anticipated. If they should occur they would be considered an unanticipated adverse event and managed as such. If the Subject has any questions or concerns about their medical condition or if an unforeseen event should occur the subject will be advised to contact the PIs or their designate.

SITE TRAINING PLANS

Training to be conducted can be divided into two pertinent categories. First is training on use of the Pulse TX System from a technical and clinical perspective. The PIs and their designated assistants will be instructed in aspects of set up, application, management and maintenance of the Pulse TX System. Those persons conducting the training will be Pulse Bioscience technical experts in this area of expertise. A select group of these experts will be present during the testing sessions to provide support as needed. Training will include a dry run. The second category is training in the clinical study requirements and processes. The study team members at the Study Site will be trained via the pertinent documents and files as well as the planned logistics to perform the study according to the protocol and applicable IRS, GCP and Pulse requirements.

INSTITUTIONAL REVIEW BOARD OVERSIGHT

The following Institutional Review Board will be asked to review and approve the proposed study:

Biomedical Research Institute of America
[name]
[name]
T - [name]
F - [name]

If the Subject has any questions or concerns about the study process, they will be advised to contact Biomed at [contact]

STUDY MANAGEMENT AND MONITORING PLAN

Pulse Biosciences, and/or their designated representatives are solely responsible for the proposed study. Pulse will take the necessary steps to assure that the study is conducted in accordance with all regulating authorities as well as applicable Standard Operating Procedures. The Study Monitor will oversee the conduct of the study on a continual basis. Minimal Monitoring visits will be conducted at the following intervals: Site Qualification Visit, Study Initiation Visit, Interim Study Visit and Study Close-Out Visit.

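### The stated 91% power belongs to a test against 51% that no success criterion uses; at the powered 65% rate, a criterion is met only about half the time

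*Combined protocol and SAP*

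**What the plan says.** The Success Criteria section sets three criteria, each at 65%.

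- Independent photographic review (the primary endpoint): "The study will be considered a success if 65% of treated lesions are reduced by a score of 2 or more points".
- Physician assessment: "Success for this criteria is 65% of lesions rated as a 0 or 1 on the scale".
- Patient assessment: 65% of lesion areas in the two best satisfaction categories.

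The overall rule is: "The overall study will be considered a success if 2 of the 3 criteria listed above are met". No criterion names a null value, a test or a confidence limit.

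The Sample Size Estimate describes something else: a one-group chi-square test whose 0.05 "two-sided significance level will have 91% power to detect the difference between the Null hypothesis proportion" of 51% and an alternative "of 0.650 (65%) when the sample size is 135". The 51% appears nowhere else in the supplied text.

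Analytical Methods lists chi-square tests and exact 95% confidence levels in general terms. It adds "Exact probabilities will be computed for any inferential analysis performed" and "All analysis will be adjusted for the correlated nature of the data". It links none of these to 51% or to the success decision. Study Design caps enrolment: "A total of up to 60 Subjects will be consented and enrolled". Study Procedure fixes three treated lesions per subject.

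**The concern.** The one power figure in the supplied text is attached to a different decision from the one that declares success. Someone who reads 91% power next to a 65% alternative, and then a 65% success bar, will expect the study to succeed about nine times in ten if the device clears 65% of lesions. It will not. When the bar sits at the true rate, the chance of reaching it is near one half, and more lesions do not help.

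There is also a band of results that would be significant against 51% and still miss 65%. The Success Criteria section settles that such a result does not meet the criterion. What the plan leaves open is what the test against 51% is for, and that is better settled before the data are seen.

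**Working it through.** **Inputs.** From the Sample Size Estimate: p0 = 0.51, pA = 0.65, two-sided alpha 0.05, n = 135. From Success Criteria: a 65% bar and two of three criteria. From Study Design and Study Procedure: up to 60 subjects with 3 treated lesions each, so up to 180 lesions.

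**Assumptions.** The 135 counts treated lesions (45 subjects × 3); the unit is not stated. All lesions are evaluable. The plan gives no within-subject correlation (ICC), so 0 to 0.5 is shown.

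**1. The plan's own figure.** Power = Φ[(pA − p0 − 1.96·√(p0(1−p0)/n)) / √(pA(1−pA)/n)].

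- √(0.51 × 0.49/135) = 0.04302, and 1.96 times this is 0.0843.
- √(0.65 × 0.35/135) = 0.04105.
- (0.14 − 0.0843)/0.04105 = 1.356, and Φ(1.356) = 0.912.

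The 91% is reproduced for 135 independent lesions.

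**2. Where the two bars lie.** The test rejects 51% when the observed rate exceeds 0.51 + 0.0843 = 0.594, that is, from 81/135 (60.0%). The criterion needs 0.65 × 135 = 87.75, so 88/135. At 180 lesions the counts are 105 for the test (106 by exact binomial tail) and 117 for the criterion.

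**3. Chance of meeting one criterion.** With independent lesions this is the exact binomial tail P(X ≥ r). With clustering, each subject's three lesions are beta-binomial and subjects are summed by exact convolution.

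| True rate | n (count needed) | ICC 0 | 0.1 | 0.3 | 0.5 |
|---|---|---|---|---|---|
| 65% | 135 (88) | 52.2% | 52.1% | 52.0% | 51.9% |
| 65% | 180 (117) | 53.4% | 53.2% | 52.9% | 52.7% |
| 70% | 135 (88) | 90.4% | 88.4% | 85.0% | 82.4% |
| 70% | 180 (117) | 93.7% | 91.9% | 88.7% | 86.2% |

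Across every whole number of subjects from 45 to 60, at a true 65% with independent lesions, the value runs from 47.5% (n = 177, 116 needed) to 53.4% (n = 180). At a true 75% it is 97% or more at n = 135 and n = 180 for ICC 0 to 0.5.

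**4. Two of three criteria.** If all three true rates are 65% and the criteria are independent, the chance is 3q² − 2q³, where q is the chance of meeting one. With q = 0.5216 this is 53%; with q = 0.5342, 55%; with q = 0.4749 (n = 177), 46%. Perfectly dependent criteria would give q itself. The rule therefore stays near one half. The documents give no planned rate for the physician and patient ratings, so equal rates are an assumption.

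**5. Results between the two bars.** The probability of rejecting 51% but missing 65%, with the test's critical count adjusted by the design effect 1 + 2·ICC:

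| True rate | n | ICC 0 | 0.1 | 0.3 | 0.5 |
|---|---|---|---|---|---|
| 65% | 135 | 38% | 33% | 21% | 15% |
| 65% | 180 | 44% | 40% | 32% | 24% |
| 70% | 135 | 9% | 10% | 10% | 8% |
| 70% | 180 | 6% | 8% | 10% | 10% |

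These hold for n = 135 and n = 180 only. At n = 177 and a true 70%, the figure is 12.5% at ICC 0.3 and at ICC 0.5.

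**6. False-positive side.** At a true 51% the 65% bar is met with probability 0.06% (n = 135) or 0.01% (n = 180), rising to 1.1% and 0.4% at ICC 0.5.

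**The case against.** The strongest reply is that nothing here is contradictory. A study may be sized on a test against a null value and separately require a minimum observed rate. The Sample Size Estimate claims only power to detect a difference between 51% and 65%, and never calls 91% the probability of study success. Analytical Methods lists chi-square tests, so the test has a possible home. All of this stands: the defect is a missing link between the two sections, not two statements that cannot both be true.

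It is also fair to say that 65% is the sizing alternative and that no passage calls it the expected rate. At 70% or 75% the chance of meeting a criterion is good. But 65% is the only alternative the supplied text gives, and it is the one to which the 91% is attached.

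Two stronger readings are tempting, and the documents do not support them. A reader might infer that a result between 81/135 and 87/135 has no prespecified interpretation. It has one: under Success Criteria it does not meet that criterion, and missing one criterion is not a failed study, because two of three suffice. A reader might also infer a risk of false success. The 65% bar is stricter than the powered test, so that does not follow.

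Subject Recruitment and Selection points to a statistical discussion in Attachment D that is not in the supplied copy. It may explain the 51%, and its absence is not counted against the plan.

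**Conclusion.** The point holds as a mismatch between the stated power and the decision rule. The 91% is correct for a test that no criterion uses. At the alternative that was powered, one criterion is met about half the time (47.5–53.4% for 45 to 60 whole subjects with independent lesions, and little changed by ICC 0.1 to 0.5). The two-of-three rule does not rescue this if all three true rates are 65%.

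The conclusion rests on reading 65% as an observed proportion, which is the plain reading when no test or limit is attached. If 65% had to be exceeded with confidence, success at a true 65% would be less likely still. It also assumes lesions as the unit and three evaluable lesions per subject.

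The harm is an over-optimistic figure and an unstated role for the test against 51%. It should be fixed, but it does not invalidate the success rule. The primary criterion's two lesion-level descriptions (final score of 0 or 1, and a 2-point reduction) are a separate matter and play no part here.

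**What to change.** Keep the 65% rule and replace the sample-size paragraph with wording such as:

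> The 91% applies only to the one-group test against 51% with 135 independent lesions. The success criteria require an observed proportion of at least 65% of evaluable lesions (for example 88 of 135, or 117 of 180). If the true rate is 65%, the chance of meeting a criterion is about one half. If it is 70%, the chance is about 82–90% (n = 135) or 86–94% (n = 180), for assumed within-subject correlation from 0.5 to 0.

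Then add one sentence: the test against 51% is supportive and does not override the Success Criteria.

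The counts should remain examples. Enrolment is up to 60, both intent-to-treat and per-protocol sets are planned, nothing is imputed, and the three criteria word their denominators differently.

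The cost is wording only, with no extra subjects and no changed threshold. The downside is that the stated chance of success becomes less favourable. Making rejection of 51% the success rule instead would be a different claim with a lower observed bar (81 rather than 88 of 135 with independent lesions), and this correction does not need it.

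### The 2-of-3 success rule lets the two secondary ratings carry the study when the primary endpoint, the independent photographic review, is missed

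*Combined protocol and SAP*

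**What the plan says.** Under Primary Endpoint, the protocol states: "The primary endpoint of the study is the degree of clearing of benign SK lesions as rated by the independent reviewer's assessment of photographs", at the final visit. Under Secondary Endpoints, it states: "A secondary endpoint of the study is the degree of clearing by the final visit as rated by the treating physician's assessment", and then "An additional secondary endpoint of the study is subject satisfaction with the SK's area at the final study visit". No other primary endpoint is defined.

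Success Criteria has four bullets.

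- First (independent review): a lesion scoring 0 or 1 at last follow-up is a success. Then: "The study will be considered a success if 65% of treated lesions are reduced by a score of 2 or more points".
- Second (physician): "Success for this criteria is 65% of lesions rated as a 0 or 1 on the scale".
- Third (subject): "Success for this criteria will be 65% of lesion areas evaluated as" being in one of the top two satisfaction categories.
- Fourth: "The overall study will be considered a success if 2 of the 3 criteria listed above are met".

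Study Design describes the trial thus: "A prospective, randomized, open label, multi-site, NSR study design where each subject serves as his or her own control will be employed". Attachment C has photographs reviewed by people outside the study, masked to time interval, energy setting, tip size and subject identifiers, and gives reduction of bias as a reason for the review. No masking is described for the physician or subject ratings. No section makes the photographic criterion a condition of overall success.

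**The concern.** The last bullet counts the three criteria equally, so the two secondary ratings already make two of three. The study could be declared a success on open-label ratings by the treating physician and the subject while the endpoint named as primary, and built to limit bias, is missed.

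There is also a problem of wording. The second and third bullets define success for a criterion; the first speaks of success for the study. If only the photographic criterion is met, the first bullet read literally says success and the fourth does not. If only the two secondary criteria are met, the first bullet is silent and the fourth says success.

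**Working it through.** **The plan's own figure.** Sample Size Estimate gives 91% power for a one-group test of 51% against 65%, two-sided 0.05, n = 135. Standard errors are √(0.51 × 0.49/135) = 0.0430 and √(0.65 × 0.35/135) = 0.0411. Power = Φ[(0.14 − 1.96 × 0.0430)/0.0411] = Φ(1.356) = 91.2%. It reproduces, but it describes one test and not the 2-of-3 rule.

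**Inputs.** Three treated lesions per subject (Study Procedure) and up to 60 subjects (Study Design) give at most 180 treated lesions. I also use 135, taking the sample-size figure as lesions, since its unit is not stated. I read 65% as at least 65% of treated lesions: 0.65 × 180 = 117, and 0.65 × 135 = 87.75, so 88. Assumptions: the true rates, one reviewer result per lesion, complete data, independent lesions and independent ratings.

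**Chance that one criterion is met**, P(Binomial(n, p) ≥ 117 or 88):

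| True rate | n = 180 | n = 135 |
|---|---|---|
| 51% | 0.0001 | 0.0006 |
| 60% | 0.0973 | 0.1263 |
| 65% | 0.5342 | 0.5216 |
| 70% | 0.9372 | 0.9044 |
| 75% | 0.9990 | 0.9959 |

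**Success with the primary failed.** With a, b, c the chances that the reviewer, physician and subject criteria are met, this is (1 − a)bc.

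| Reviewer v both others | n = 180 | n = 135 |
|---|---|---|
| 60% v 60% | 0.9% | 1.4% |
| 65% v 65% | 13% | 13% |
| 70% v 70% | 5.5% | 7.8% |
| 75% v 75% | 0.1% | 0.4% |
| 60% v 65% | 26% | 24% |
| 60% v 70% | 79% | 71% |
| 51% v 65% | 29% | 27% |
| 70% v 65% | 1.8% | 2.6% |

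Examples at n = 180: all at 65%, 0.4658 × 0.5342² = 0.133; 60% v 70%, 0.9027 × 0.9372² = 0.793. With equal rates the expression is (1 − a)a², which cannot exceed 4/27 = 14.8% (at a = 2/3).

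**Sensitivity to correlation.** A latent-normal simulation with assumed variance shares of 0.3 for subject, 0.3 for lesion and 0.4 for each rating gives, for 180 / 135 lesions, 2.3% / 3.0%, 7.9% / 7.8%, 4.5% / 5.6% and 0.4% / 0.9% at equal rates of 60%, 65%, 70% and 75%, and 71% / 63% at 60% v 70%. The pattern is unchanged.

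**Only the primary met** (first and fourth bullets disagree), a(1 − b)(1 − c): all at 65%, 0.5342 × 0.4658² = 12% (also 12% at n = 135); reviewer 70% v others 65%, 0.9372 × 0.4658² = 20% (21%).

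**All three at 51%.** The 2-of-3 rule succeeds with probability 3a² − 2a³, about 3 × 0.0006² = 0.000001 at n = 135. With correlations between ratings of up to 0.8 it stays at 0.0003 or less.

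**The case against.** The rule is explicit and prespecified, and a sponsor may choose a composite of three views. Analytical Methods plans a separate intent-to-treat analysis of the primary, so a missed primary would still be visible. Both points stand, but the declared verdict could still differ from the primary result, and the plan does not say that this is intended.

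The large probabilities all need the photographic reviewer to be harsher than both other raters, and no section suggests that direction. This stands: the equal-rate rows are the fairer starting point. The masking contrast also has limits. Attachment C does not list treated-or-control status among the masked items, it gives reviewers an identified baseline photograph, and a subject's own satisfaction could hardly be masked.

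Three stronger readings are tempting, and the documents do not support them.

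- A reader might infer that the rule inflates false success in general. It does not when all three rates are at the 51% null.
- A reader might take 51% for the reviewer and 65% for the others as the plan's own scenario. Those figures are the two hypotheses of a single test; splitting them between raters is only an illustration.
- A reader might conclude that the plan gives two equally valid, opposite verdicts when only the primary is met. The fourth bullet comes last, speaks of the overall study and refers back to the three criteria, so it most naturally governs. The first bullet reads as a criterion loosely worded.

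**Conclusion.** The concern holds as a matter of logic: nothing in the protocol stops the two secondary ratings from declaring success when the only primary criterion is missed. The first bullet does not prevent this, since at most it makes the primary sufficient, never necessary.

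The size is conditional. With equal true rates and independent ratings it runs from about 0.1% to 13% over the rates tried, greatest near the 65% threshold and small well away from it. It becomes large only when the reviewer's rate is below that of both other raters, and is small when the reviewer scores higher. All rates by rater are assumed, and clustering of lesions within subjects enters only through the simulation.

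**What to change.** Make the primary criterion necessary for overall success. Replace the last bullet with one of the following; either closes the gap, and the choice is the sponsor's.

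- (a) *The study succeeds if and only if the independent-reviewer (primary) criterion is met; the physician and patient criteria are supportive.*
- (b) *The study succeeds if the independent-reviewer (primary) criterion and at least one of the other two are met.*

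Reword the first bullet as a criterion: *A lesion is a success if the independent review rates it 0 or 1 at the last follow-up; the criterion is met if at least 65% of treated lesions are successes.* Do not keep the 2-point reduction unless a baseline reviewer score is collected or baseline is fixed at 3. Attachment C has reviewers score only post-treatment images, with the baseline photograph as a comparator.

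The cost is two bullets and no new subject data. The chance of success changes as follows (independent ratings, 180 lesions). The current rule is (1 − a)bc + a[1 − (1 − b)(1 − c)], option (a) is a, and option (b) is a[1 − (1 − b)(1 − c)].

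| All true rates | Current | (a) | (b) |
|---|---|---|---|
| 60% | 2.7% | 9.7% | 1.8% |
| 65% | 55% | 53% | 42% |
| 70% | 99% | 94% | 93% |

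Option (a) can raise the chance of success when all rates are below target. Option (b) never exceeds the current rule, but costs more at 65%. How the ratings of two or three reviewers are combined is a separate matter.
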